8.0 Duration of Therapy and Stopping Rules

8.1 Stopping Rules for individual subject

In the absence of treatment delays due to adverse events, treatment may continue for 3 cycles or until one of the following criteria applies:

- Cumulative renal radiation dose exceeds 23 Gy.
- Intercurrent illness prevents further administration of treatment.
- Unacceptable adverse event(s) such as irreversible renal or hematopoietic toxicity.
- Initiation of another tumor specific therapy.
- Patient decides to withdraw from the study.
- General or specific changes in the patient's condition render the patient unacceptable for further treatment in the judgment of the investigator.

Other causes of discontinuation from study:

- Termination of study by Sponsor.
- Subject's condition no longer requires study drug.

* Note: Disease progression alone does not mandate discontinuation of ⁹⁰Y treatment.*

Disease progression per RECIST 1.1 criteria during the follow up period will warrant removal from study.

8.2 Stopping Rules for Trial

Enrollment will proceed according to a Simon two-stage study design. Thirty-five subjects will be enrolled in the first stage; if 5 or fewer patients respond (Stable, PR or CR) as determined by ⁶⁸Ga-DOTATOC PET/CT and diagnostic CT or MRI (RECIST 1.1 criteria), the study will be closed and the treatment ruled clinically uninteresting. Otherwise, an additional 29 subjects will be enrolled. If 20 or more responses are observed in the total of 64 subjects, then the treatment will be ruled worthy of further study.

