4.0 Objectives

4.1 Primary Objectives

1. Quantify number of CR, PR, MR, SD and progressions in response to dosimetry-guided PRRT utilizing RECIST 1.1 criteria and ⁶⁸Ga-DOTATOC or ⁶⁸Ga-DOTATATE PET to evaluate efficacy of ⁹⁰Y-DOTATOC therapy in children and adults with neuroendocrine and other somatostatin receptor positive tumors.
2. Monitor renal, hematologic, and clinical toxicities associated with dosimetry-guided ⁹⁰Y-DOTATOC PRRT while maximizing total tumor dose and limiting total renal dose of ⁹⁰Y-DOTATOC to ≤ 23 Gy.

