6.0 Imaging and Treatment Plan

**Phase II,
Dosimetry-Guided, Peptide Receptor Radiotherapy (PRRT) with
⁹⁰Y-DOTA-tyr³-Octreotide (⁹⁰Y-DOTATOC) in Children and Adults
with Neuroendocrine and other Somatostatin Receptor Expressing Tumors**

Treatment Cycles and Followup		Imaging and Treatment Schedule	Initial ⁹⁰ Y-DOTATOC Dose	Cumulative ⁹⁰ Y-DOTATOC Dose	Cumulative Renal Radiation
Cycle 1 Week 1	Day 1	Physical exam with height, weight, vitals, labs, list, GFR, pregnancy test; QOL questionnaire Start 18 hrs IV/PO fluids			
	Day 2	⁹⁰ Y-DOTATOC + IV amino acids Continue IV/PO fluids for 48 hrs	50 mCi/m ² in children; 120 mCi in adults	120 mCi maximum	
	Day 4	⁹⁰ Y-DOTATOC PET/CT			
Cycle 2 Week 7-9	Day 1	Physical exam with height, weight, vitals, labs, med list, GFR, pregnancy test Start 18 hrs IV/PO fluids			
	Day 2	⁹⁰ Y-DOTATOC + IV amino acids Continue IV/PO fluids for 48 hrs	Dosimetry determined	270 mCi maximum	
	Day 4	⁹⁰ Y-DOTATOC PET/CT			
Cycle 3 Week 13-17	Day 1	Physical exam with height, weight, vitals, labs, list, GFR, pregnancy test Start 18 hrs IV/PO fluids			
	Days 2-3	⁹⁰ Y-DOTATOC + IV amino acids Continue IV/PO fluids for 48 hrs	Dosimetry determined	420 mCi maximum	≤ 23 Gy
FU	3 months after treatment 3	Physical exam with height, weight, vitals, labs, med list, GFR; QOL questionnaire, diagnostic CT (MRI)			
	6-9 months after treatment 3	Physical exam with height, weight, vitals, labs, med list, GFR; diagnostic CT (MRI) ⁶⁸ Ga-DOTATOC PET/CT;			

Treatment consists of 3 cycles, 6-8 weeks apart. Cycle 1 dose is fixed. Cycles 2 and 3 doses will be determined by dosimetry-based calculation of renal doses from previous cycles; total renal dose ≤ 23Gy.

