Treatment efficacy, defined as a complete response, partial response or stable disease (CR+PR+SD), is the primary endpoint of interest in this dosimetry-guided Phase II trial. Tumor response will be defined according to RECIST1.1 criteria applied on up to five target lesions (primary tumor if not surgically removed, up to two liver lesions, up to two nodal metastases, metastatic lesion in other organs, such as ovary, breast) that will be quantified and compared between pre-therapy and 3-9 months post-therapy high-resolution, contrast-enhanced CTs. Osseous metastases may be followed as non-target lesions. ⁹⁰Y-DOTATOC will be deemed worthy of further study if its associated response rate is ≥ 0.60 , and clinically uninteresting if its rate is ≤ 0.40 . Enrollment will proceed according to an optimal Simon two-stage study design. Sixteen (16) subjects will be enrolled in the first stage; if 7 or fewer patients respond, the arm will be closed and the treatment ruled clinically uninteresting. Otherwise, an additional 30 subjects will be enrolled. If 24 or more responses are observed in the total of 46 subjects, then the treatment will be ruled worthy of further study. The study design has a probability of early termination equal to 0.72. Power to detect efficacy is 0.80 with a type 1 error rate of

0.05.

Secondary analysis will focus on time to tumor progression and overall survival. The method of Kaplan- Meier will be used to estimate progression and survival rates. Subjects for whom the outcome of interest is not observed at the 6 month follow-up will be treated as censored observations in the survival analysis.

12.2 Primary Objective 2

Adverse events will be recorded and reported in tabular form by type and grade. If four or more subjects experience renal toxicity \geq Grade 4, the radiopharmaceutical will be declared too toxic and the trial will be stopped. If any other irreversible Grade 4 toxicity is observed in four or more subjects, the treatment will be declared too toxic and will be stopped. Adverse events will be graded according to the most recent CTE guidelines.

12.3 Secondary Objective 1

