For subjects who participated in the ^{68}Ga -DOTATOC Comparator trial (IRB # 201212736), the number, size, and location of discordant lesions between ^{68}Ga -DOTATOC PET/CT and Octreoscan will have been tabulated. This analysis will be updated using the results of post- therapy ^{68}Ga -DOTATOC PET/CT for those patients who participated in the comparator study, but only received the initial ^{68}Ga -DOTATOC PET/CT due to progression on the Octreoscan + high-resolution, contrast-enhanced CT. Lesions that were positive on PET, but negative on Octreoscan will be considered true positive if a response to PRRT is documented after either Cycle 1 or at 6-9 month followup following last ^{90}Y -DOTATOC infusion.

For subjects who did not participate in the ^{68}Ga -DOTATOC Comparator trial, all ^{68}Ga -DOTATOC PET/CT scans will be acquired as part of this study; number, size, and location of lesions will be analyzed between first and subsequent ^{68}Ga -DOTATOC PET/CTs.

12.4 Secondary Objective 2

Compare SUVmax between primary tumor, liver lesions, and extra-hepatic lesions with expression levels of sst2 using qRT-PCR and/or receptor IHC from fresh frozen or paraffin-embedded samples where available.

Compare maximum SUVs of primary tumor, liver lesions, and extra-hepatic lesions with expression level of sst2 RNA and IHC on fresh frozen tissue, or paraffin embedded samples (block(s) or 10 unstained slides) to determine whether or not any correlation exists between SUVmax, sst2 expression, or sst2 protein and response to PRRT. The study is expected to delineate whether measurement of sst2 expression by either qRT-PCT or immunohistochemistry at diagnosis can predict response to ^{90}Y -DOTATOC. We will construct a table tabulating SUVmax, level of RNA expression, and IHC level for all lesions biopsied. With 64 subjects the correlation between SUV max, RNA expression and IHC will be determined. Analysis of SUVmax compared with sst2 RNA and receptor protein expression on primary tumor and metastatic lesions will be considered worthy of further study if $> 50\%$ of lesions demonstrate a positive correlation. Tissue will be sent to 3080 Med Lab in University of Iowa Hospital and Clinics for analysis.

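### Sections 8.2 and 12.1 set two incompatible Simon two-stage designs (64 and 46 subjects) for the same CR+PR+SD endpoint, and nothing says which governs

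*Combined protocol and SAP*

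**What the plan says.** All of the text below is operative text of the combined protocol and SAP, version 5.

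- **Section 8.2 (Stopping Rules for Trial).** First stage: "Thirty-five subjects will be enrolled in the first stage; if 5 or fewer patients respond (Stable, PR or CR". If the trial continues, 29 more subjects are added. "If 20 or more responses are observed in the total of 64 subjects, then the treatment will be ruled worthy of further study". No null rate, alternative, error rate or power is given.
- **Section 12.1 (Primary Objective 1).** First stage: "Sixteen (16) subjects will be enrolled in the first stage; if 7 or fewer patients respond, the arm will be closed". If it continues, 30 more are added, and success is declared as follows: "If 24 or more responses are observed in the total of 46 subjects". The hypotheses are 0.40 (of no interest) and 0.60 (worth pursuing), with type 1 error 0.05 and power 0.80. "The study design has a probability of early termination equal to 0.72".
- **Section 12.4 (Secondary Objective 2)** takes the larger size: "With 64 subjects the correlation between SUV max, RNA expression and IHC will be determined".

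Both rules count CR, PR and SD as response, but how response is read differs:

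- Section 4.1 sets out to "Quantify number of CR, PR, MR, SD and progressions in response to dosimetry-guided PRRT utilizing RECIST 1.1 criteria and" 68Ga PET.
- Section 8.2 uses 68Ga PET/CT together with diagnostic CT or MRI under RECIST 1.1.
- Section 12.1 applies RECIST 1.1 to contrast-enhanced CT taken 3 to 9 months after therapy.

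In the Section 6.0 schedule the imaging at the 3-month visit is only "QOL questionnaire, diagnostic CT (MRI"). The 68Ga PET comes at 6-9 months, and the Section 7.0 calendar agrees.

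**The concern.** No sentence assigns the two designs to different cohorts or endpoints, or ranks one above the other. They differ in first-stage size, futility cut-off, total size and success cut-off.

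The success bar in 8.2 is 20/64 = 31%, below the 40% that 12.1 treats as the rate of no interest. Its futility bar is 5/35 = 14%. The rules can also collide on the same subjects. With 6 or 7 responses among the first 16, 12.1 closes the trial. Under 8.2 the same count already clears the first-stage bar of 5, whatever the next 19 subjects do.

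If this is left open, the sample size, the futility decision and the primary conclusion could be settled after responses are known. Because 8.2 carries the trial stopping-rule heading, it is where a team or monitor would look first, and it is the version with no stated operating characteristics.

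**Working it through.** **Inputs**

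| | First stage n1 | Close if ≤ r1 | Total n | Success if ≥ r |
|---|---|---|---|---|
| Section 12.1 | 16 | 7 | 46 | 24 |
| Section 8.2 | 35 | 5 | 64 | 20 |

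Hypotheses (12.1 only): p0 = 0.40, p1 = 0.60.

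**Formulas** (exact binomial; X1 from n1 subjects, X2 from n − n1)

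- Early termination = P(X1 ≤ r1).
- P(success) = sum over x from r1+1 to n1 of P(X1 = x) × P(X2 ≥ r − x).

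**Step 1: reproduce 12.1**

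- Early termination at 0.40: P(X1 ≤ 7 of 16) = 0.716 (stated 0.72).
- P(success) at 0.40 = 0.0486 (stated 0.05).
- P(success) at 0.60 = 0.8006 (stated 0.80).
- Expected size at 0.40: 16 + (1 − 0.716) × 30 = 24.5.

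A search over two-stage designs for these inputs returns this one as the Simon optimal design. Section 12.1 is correct on its own terms.

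**Step 2: both rules across true rates**

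| True rate | 8.2 early stop | 8.2 success | 12.1 early stop | 12.1 success |
|---|---|---|---|---|
| 0.20 | 0.272 | 0.022 | 0.993 | 0.000 |
| 0.30 | 0.027 | 0.460 | 0.926 | 0.001 |
| 0.40 | 0.001 | 0.942 | 0.716 | 0.049 |
| 0.50 | 0.000 | 0.999 | 0.402 | 0.360 |
| 0.60 | 0.000 | 1.000 | 0.142 | 0.801 |

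**Step 3: what hypotheses would suit 8.2?** Its success probability equals 0.05 at a true rate of 0.218 and 0.80 at 0.355. The plan states neither rate.

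**Step 4: can 35 then 64 be kept for 0.40 against 0.60?** Closing at ≤ 15 of 35 and requiring ≥ 33 of 64 gives early termination 0.700, type 1 error 0.038, power 0.921 and expected size at 0.40 of 35 + (1 − 0.700) × 29 = 43.7. A single-stage test at 64 also needs ≥ 33 (type 1 error 0.040, power 0.933). This shows how far 20 of 64 is from a cut-off suited to those hypotheses.

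**The case against.** Four points can be made for the plan.

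1. **No stated figure is wrong.** The numbers in 12.1 reproduce, and 8.2 gives none. The 0.942 pairs the cut-offs of 8.2 with the null of 12.1, which neither section does. This is true, and the figure must be read as conditional. The conflict does not depend on it.
2. **The verdicts may agree in practice.** Section 1.4 reports 20-30% partial responses and more than 50% stable disease with this class of therapy, which suggests CR+PR+SD of about 0.70 or higher. At 0.70, success has probability 0.972 under 12.1 and about 1.000 under 8.2. This is a fair limit on the likely effect on the final verdict. But the trial also admits other tumour types, the sample size and timing of the look still differ, and a stopping rule exists for the case where the expectation fails.
3. **The response readings need not clash.** Section 8.2 names no visit, and both 68Ga PET/CT and CT or MRI are scheduled at 6-9 months, inside the 12.1 window. This stands. The narrower point remains that at 3 months only the 12.1 reading is possible, and neither the role of PET nor the visit that counts is fixed.
4. **The intended size is unknown.** The figure 64 appears in two sections and 46 in one. This stands too, and is why the fix offers alternatives.

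**Conclusion.** The concern holds and must be fixed. Two operative designs govern the same endpoint and cannot both be followed.

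Under the only hypotheses the plan states, the 12.1 rule controls error at 0.049 with power 0.801. The 8.2 rule passes a treatment at the 40% null with probability 0.942 and almost never stops for futility (0.001). At a true rate of 0.50 the chance of a positive verdict is 0.999 under 8.2 and 0.360 under 12.1. The 8.2 rule does discriminate at lower rates, around 0.22 against 0.36, but the plan gives no such hypotheses.

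These figures assume independent subjects with a common response rate, all evaluable, and success cut-offs read as written (at least 20, at least 24). The contradiction itself rests on the text alone. One passage of the document was not available for this review, and the documents do not show enrolment status.

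**What to change.** Name one governing design and align 8.2, 12.1 and 12.4 with it.

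- **Default: 12.1.** Put 16 (close at ≤ 7) and 46 (success at ≥ 24) into 8.2, and change 64 to 46 in 12.4. It is the only design with stated hypotheses, and it delivers them.
- **If 64 is intended:** recompute the cut-offs for 0.40 against 0.60 and restate early termination, error and power. The rule ≤ 15 of 35 and ≥ 33 of 64 is one workable example; it has not been shown to be optimal.
- **If the 8.2 cut-offs are intended:** state and justify their null and alternative, and remove 0.40 and 0.60 from 12.1.

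In each case, use one definition of response in 4.1, 8.2 and 12.1: the role of RECIST on CT or MRI, the role of 68Ga PET, and the visit that counts.

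**Cost.** If no interim look has been passed, this is a text amendment. If one has, the amendment must record which data had been seen.

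Two knock-on effects follow if 46 governs:

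- Section 12.4 loses 64 − 46 = 18 subjects. As an illustration, assuming a correlation of 0.5 and one independent pair per subject, the 95% interval tanh(atanh 0.5 ± 1.96/√(N − 3)) widens from 0.29-0.66 to 0.25-0.69. The 12.4 analysis is by lesion, so this is only a guide.
- The toxicity rule in 12.2 is a fixed count of four with no denominator, so its chance of triggering depends on N. For assumed true event rates of 2%, 5% and 10%, P(at least 4 events) is 0.039, 0.399 and 0.894 at N = 64, and 0.013, 0.197 and 0.688 at N = 46. Its properties should be restated for the chosen size.

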9.0 Regulatory and Reporting Requirements

The Data and Safety Monitoring Committee (DSMC) of the Holden Comprehensive Cancer Center will provide data and safety monitoring for this study. "The Data and Safety Monitoring Plan of the Holden Comprehensive Cancer Center" provides standard operating procedures to monitor all clinical cancer trials at the UIHC. All investigator-initiated trials are automatically monitored by the DSMC. The Data Safety and Monitoring Plan for this risk level 4 study is attached as Appendix 1.

9.1 Adverse Events List and Reporting Requirements

As with any new drug, this study may involve risks that are currently unforeseeable. The most frequent adverse events observed in adults treated with these drugs are listed below.

Severity of adverse events will be graded according to NCI Common Terminology Criteria for Adverse Events version 4.0 (CTCAE v4.0) which is available at <http://ctep.cancer.gov/reporting/ctc.html>.

Adverse events will be collected from time of consent until 30 days post ⁹⁰Y treatment. Labs will only be collected as adverse events if deemed clinically significant by the investigator. Serious Adverse Events (SAE's) that occur >30 days after the last ⁹⁰Y treatment will only be reported if at least possibly related to investigational product.

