9.1.2 Expedited Adverse Event Reporting to DSMC

Serious adverse events occurring during study procedures with ^{90}Y -DOTATOC will require a notification to the DSMC as described in the Data and Safety Monitoring Plan (see appendix 1) below regardless of attribution to study intervention. The investigator will continue to follow or obtain documentation until the resolution of such an event until it is resolved (with or without sequelae)

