9.1.3 Adverse Event Reporting Guidelines –

Documentation will begin after radiotracer injection and continue through 1 calendar day following imaging. This study will use the guidelines developed by the Cancer Therapy Evaluation Program (CTEP) for PET and/or SPECT IND agents. For purposes of the below table, it should be noted that the radioactive half-life for ^{90}Y is 64.1 hours. Therefore, 10 radioactive half-lives will be 27 days for the purposes of adverse event reporting.

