An independent study monitor and/or the DSMC Chair (or designee), will review study data (provided by the PI/available in OnCore) and communicate with the PI at least biannually. A copy of this communication will be forwarded to the DSMC and PRMC Chairs.

Additional Reporting Requirements:

- A scanned copy of the completed eligibility checklist, with screening information and signature from evaluating study team member, will be attached in OnCore for ongoing review by DSMC staff.
- Serious adverse events will be entered directly into an OnCore SAE report by the research team. OnCore will send an automatic notification to the DSMC Chair/acting Chair and staff for review.

- The DSMC utilizes a risk-based monitoring approach. The trial's research records will be monitored at minimum twice per year. Monitoring may be done more frequently depending on the protocol, risks to subjects, reported serious/adverse events, patient population and accrual rate. Records for a minimum of 25% of subjects will be monitored for the entire study.

Monitoring will involve the following:

- review eligibility of patients accrued to the study,
- check for the presence of a signed informed consent,
- determine compliance with protocol's study plan,
- determine whether SAEs are being appropriately reported to internal and external regulatory agencies,
- compare accuracy of data in the research record with the primary source documents,
- review investigational drug processing and documentation,
- assess cumulative AE/SAE reports for trends and compare to study stopping rules.

Routine Adverse Event Reporting

For non-serious Adverse Events, documentation will begin after radiotracer injection and continue through 1 calendar day following imaging. For studies using PET or SPECT IND agents, the AE reporting period is limited to 10 radioactive half-lives, rounded UP to the nearest whole day, after the agent/intervention was last administered. [⁹⁰Y is 64.1 hours. Therefore, 10 radioactive half-lives will be 27days].

Collected information should be recorded in the electronic/Case Report Forms (eCRF/CRF) for that subject. A description of the event, its severity or toxicity grade, onset and resolved dates (if applicable), and the relationship to the study drug (if a grade 3 or higher) should be included. Documentation should occur in real time.

Serious Adverse Event Reporting

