For any experience or condition that meets the definition of a serious adverse event (SAE), recording of the event will begin after radiotracer injection and continue through 1 calendar day following imaging. For studies using PET or SPECT IND agents, the AE reporting period is limited to 10 radioactive half-lives, rounded UP to the nearest whole day, after the agent/intervention was last administered. [⁹⁰Y is 64.1 hours. Therefore, 10 radioactive half-lives will be 27days]

Investigators must report to the DSMC any serious adverse events (SAE), whether or not they are considered related to the investigational agent(s)/intervention (21 CFR 312.64). SAEs must be reported via an OnCore SAE Report within 1 business of learning of the event.

An adverse event is considered **serious** if it results in ANY of the following outcomes:

1. Death
2. A life-threatening adverse event
3. An adverse event that results in inpatient hospitalization OR prolongation of existing hospitalization for ≥ 24 hours

4. A persistent or significant incapacity or substantial disruption of the ability to conduct normal life functions
5. A congenital anomaly/birth defect.
6. Important Medical Events (IME) that may not result in death, be life threatening, or require hospitalization may be considered serious when, based upon medical judgment, they may jeopardize the patient or subject and may require medical or surgical intervention to prevent one of the outcomes listed in this definition. (FDA, 21 CFR 312.32; ICH E2A and ICH E6).

Data Monitoring and Management

All studies that undergo PRMC review and/or utilize HCCC Clinical Research Services (CRS) resources are required to register subjects in OnCore. Subject registration includes the following:

- Consent date and the IRB approved consent used
- Date of eligibility and eligibility status (eligible, not eligible)
- On study date and subject's disease site (and histology if applicable)
- On treatment date (if applicable)

If/when eCRFs are developed for this study, the following data monitoring strategy will be used:

Subject Data

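### The adverse event windows in section 9.1 conflict with those in 9.1.3 and Appendix II, and all of those for non-serious events close before the follow-up visits where late renal and marrow toxicity would be seen

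*Combined protocol and SAP*

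**What the plan says.** **Section 9.1.** "Adverse events will be collected from time of consent until 30 days post" 90Y treatment. Serious events more than 30 days after the last treatment "will only be reported if at least possibly related to investigational product"; no end date is set. Laboratory values become adverse events only if the investigator judges them clinically significant. Grading is by CTCAE v4.0.

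**Section 9.1.2.** "Serious adverse events occurring during study procedures with" 90Y-DOTATOC are notified to the DSMC whatever their attribution. No number of days is given, and the reader is sent to the monitoring plan.

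**Section 9.1.3.** "Documentation will begin after radiotracer injection and continue through 1 calendar day following imaging". The same paragraph adds that "10 radioactive half-lives will be 27 days for the purposes of adverse event reporting".

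**Appendix II (monitoring plan).** For non-serious events it repeats both limits: the day after imaging, and "the AE reporting period is limited to 10 radioactive half-lives, rounded UP to the nearest whole day, after the agent/intervention was last administered", worked out as 27 days. For serious events "recording of the event will begin after radiotracer injection and continue through 1 calendar day following imaging", followed by the same 27-day limit. The next paragraph has no time limit: "Investigators must report to the DSMC any serious adverse events (SAE), whether or not they are considered related" to the study agent.

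**Section 7.0 calendar.** Adverse event assessment, blood tests (including blood count and creatinine) and GFR if indicated are marked at both the 3-4 month and the 6-9 month follow-up.

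**Section 9.2** warns that kidney damage may appear months after the last dose.

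**Section 12.2** tabulates adverse events by type and grade. It stops the trial if four or more subjects have renal toxicity of Grade 4 or higher, or another irreversible Grade 4 toxicity. It names no window and refers to the latest grading guideline rather than to v4.0.

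**The concern.** Monitoring renal, hematologic and clinical toxicity is Primary Objective 2 (section 4.1), and the 12.2 table and four-subject rules are its whole stated analysis. What enters that analysis depends on the collection window, and the windows disagree on start, on end and on late serious events. The toxicity the protocol most expects to be delayed is looked for at scheduled visits, at a time when no non-serious window is open. Two teams following different sections could report different toxicity tables from the same patients. The DSMC is also to compare cumulative event reports with the stopping rules (Appendix II), so the ambiguity reaches its input too.

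**Working it through.** **1. The plan's own figure.** 10 × 64.1 h = 641 h; 641/24 = 26.7 days, rounded up to 27. This reproduces.

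**2. The imaging-based end.** Section 6.2 places the 90Y PET/CT 40 to 56 h after dosing. Adding one day gives 2.7 to 3.3 days, so about 3 days after the dose. After Cycle 3 this end is uncertain. The calendar marks Cycle 3 dosimetry, but the treatment schema shows no Cycle 3 scan and section 10.1 acquires dosimetry after treatments 1 and 2 only.

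**3. The windows side by side.**

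| Source | Start | End, non-serious | End, serious |
|---|---|---|---|
| 9.1 | consent | 30 days | none if possibly related |
| 9.1.2 | – | – | no day count; defers to the plan |
| 9.1.3 | injection | day after imaging; also 27 days | not separated |
| Appendix II | injection | day after imaging; also 27 days | the same limits, then any serious event with no date |

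Section 9.1.3 and Appendix II agree with each other. The conflict is between them and 9.1, and between the two ends that each of them gives.

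**4. Gap to the follow-up visits.** Gap = months × 365.25/12 − window length, counted from the last treatment. Three, four, six and nine months are 91.3, 121.8, 182.6 and 273.9 days.

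| Window | 3-4 month visit | 6-9 month visit |
|---|---|---|
| 30 days | 61.3 to 91.8 days after closing | 152.6 to 243.9 |
| 27 days | 64.3 to 94.8 | 155.6 to 246.9 |

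If three calendar months are 89 to 92 days, the smallest gap is 59 to 62 days.

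**5. Assessments after the last infusion.** The calendar's adverse event row is marked at baseline, C1D1, C1D2, C2D1, C3D1, 3-4 months and 6-9 months. After the C3D2 infusion only the last two remain, and both lie outside every non-serious window.

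**6. Two cases traced through the text.**
- *Non-serious creatinine rise first seen at 3-4 months.* It is found at a scheduled assessment but is outside the 30-day, 27-day and imaging-based windows. It must also pass the clinical-significance test in 9.1. Nothing in 12.2 says whether it is tabulated.
- *Possibly related serious renal event at 6 months.* It is reportable under 9.1, outside the 27-day limit in Appendix II, and reportable again under that appendix's next paragraph. If it is Grade 4 or higher, the wording of 12.2 counts it.

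**7. Illustration only: the four-subject rule if late events went uncounted.** P(X ≥ 4), X ~ Binomial(n, rate × share counted). The rates and shares are assumed; n is 46 (section 12.1) or 64 (section 8.2).

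| Assumed rate | n = 46, all counted | n = 46, half counted | n = 64, all counted | n = 64, half counted |
|---|---|---|---|---|
| 5% | 0.197 | 0.028 | 0.399 | 0.076 |
| 10% | 0.688 | 0.197 | 0.894 | 0.399 |

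At 2% the rule is rarely met even with full counting (0.013 and 0.039). The nearest documentary figure is section 13.3: none of 58 patients (18 + 40) had irreversible renal toxicity. The one-sided 95% upper bound is 1 − 0.05^(1/58) = 0.050, but that endpoint is not Grade 4 or higher toxicity.

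**The case against.** A 30-day general window with later related serious events retained is a legitimate design choice. The late assessments also have a purpose under it, since they can detect and follow those serious events. That stands: the late visits do not by themselves contradict 9.1.

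A reader might infer that four sections give four rival rules. The text does not go that far. Section 9.1.2 sets no number of days and defers to the monitoring plan, and 9.1.3 matches that plan.

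A reader might also infer that late Grade 4 renal events escape the four-subject rule. The documents do not support this. The rule counts subjects who *experience* such toxicity, with no cut-off. Section 9.1 keeps late related serious events, one paragraph of Appendix II requires any serious event to be reported, and reviewers see study data as well as event reports. Excluding those events requires reading the 27-day limit over all of this. The binomial figures show only what that strict reading would do at assumed rates, and they do not carry the point.

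It could be argued that the half-life limit was meant for imaging agents only. But 9.1.3 adopts those guidelines for this study and computes the limit from the half-life of 90Y, the therapeutic isotope.

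None of this answers the gap for late non-serious events.

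**Conclusion.** The point holds in two parts. First, section 9.1 conflicts with 9.1.3 and Appendix II on when collection starts and ends, and with the Appendix II limit on late serious events. Second, as written, late non-serious renal and hematologic decline falls outside every non-serious window, by about 61 days or more at the first follow-up visit, and so may be left out of the Primary Objective 2 table. The gap assumes average months and a 30-day count from the last treatment; 9.1 says *last* for serious events but not for adverse events in general.

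For the four-subject rule the conclusion is narrower. Late Grade 4 or higher renal events are included on its plain wording, but one passage read strictly would not record them, so 12.2 should say that they count. How many events are affected cannot be estimated from the documents. This should be fixed, but it does not show that the stopping rule fails or that late safety is unmonitored.

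**What to change.** 1. Use one general window, consent to 30 days after the last 90Y treatment, in 9.1, 9.1.3 and Appendix II. It contains the others. Delete the tracer-imaging and 27-day wording, and carry the 9.1 provision for late, possibly related serious events into Appendix II.
2. As a stated exception, collect renal and hematologic toxicity through the 6-9 month visit.
3. In 12.2, state that scheduled creatinine, GFR (if indicated) and blood count results through that visit are graded by one named CTCAE version and enter both the table and the four-subject count. Amend the clinical-significance sentence in 9.1 so that it does not exclude them.
4. Reconcile 8.1, which removes subjects who progress during follow-up, with 10.3 and calendar footnote 8, which require follow-up after treatment ends early, so that it is clear whether the remaining safety visits are collected.
5. Clerical: 9.0 and 9.1.2 point to Appendix 1 for the monitoring plan, which is Appendix II.

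The cost is protocol and monitoring-plan wording plus some data entry; the visits and tests are already in the calendar. The downside is a few more tabulated events, some due to disease rather than drug.
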